#### Primary Endpoint

Plasma glutamine before induction to anesthesia and 24 hours after CPB, and plasma troponin I before induction to anesthesia, 5 minutes, 6 hours, 24 hours and 48 hours after CPB.

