	
Exclusion Criteria
 

– Change of surgical plan from elective into emergency CABG surgery

– Additional procedures other than coronary artery bypass graft procedure

– Onset of myocardial infarction within the last three months

– Blood creatinine level > 2 mg/dL

– ALT/AST level > 1.5x of normal value

– Use of preoperative intra-aortic balloon pump

– History of stroke with onset of less than 3 months

– Preoperative atrial fibrillation

– Heart conduction problem or pacemaker use

– Contraindications to pulmonary artery catheter insertion

 
Drop out criteria
 

– Stroke after surgery

– Perioperative myocardial infarction based on type 5 myocardial infarct criteria

– Haemorrhage complications requiring repeat surgery

– Use of continuous veno-venous hemofiltration or haemodialysis after coronary artery bypass graft surgery

– Delayed sternal closure

– Aortic cross-clamp duration of > 120 minutes and/or cardiopulmonary bypass duration of >180 minutes

Study Product, Dose, Route, Regimen	

– Glutamine Group: will receive intravenous infusion of 0.5 mg/kgbw L-alanyl-L-glutamine dipeptide (Dipeptiven, Fresenius Kabi, Bad Homburg, Germany) diluted in normal saline up to 500 mL, started after induction of anesthesia for 24 hours.

	

– Control Group: will receive intravenous infusion of 500 mL normal saline, started after induction of anesthesia for 24 hours

Statistical Methodology	
Primary Endpoint
 
Plasma glutamine before induction to anesthesia and 24 hours after CPB, and plasma troponin I before induction to anesthesia, 5 minutes, 6 hours, 24 hours and 48 hours after CPB.
 
Secondary Endpoint
 
Alpha-Ketoglutarate, myocardial injury score, apoptosis index, anti-cardiac troponin I expression, ejection fraction, cardiac index, plasma lactate, intensive care unit ventilation time, intensive care unit length of stay and vasoactive inotropic score.

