### **Goals of the study:**

To analyze the effect of intravenous glutamine in low EF patients undergoing on-pump CABG surgery in:

1. Reducing myocardial damage by a decrease of myocardial injury score, apoptotic index and increase of anti-cardiac troponin I expression through right atrial appendage tissue sample, as well as decrease of troponin I level.
2. Improving myocardial metabolism by a decrease in plasma lactate levels, increase of plasma glutamine levels and alpha ketoglutarate ( $\alpha$ -KG) levels in the right atrial appendage tissue sample.
3. Improving hemodynamic profile through an increase in EF and cardiac index after CPB
4. Reducing postoperative morbidity by the decrease of ventilator duration, duration of intensive care, and use of postoperative vasoactive and inotropes

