### **SAMPLE SIZE JUSTIFICATION**

#### **Sample size calculations**

The sample size of this study is obtained from the two-way hypothesis testing formula for the two mean values in two independent groups with a confidence index ( $\alpha$ ) of 95% and power of 80%. Results are considered statistically significant if  $p < 0.05$ . The details of the estimated size of the research subject are as follows:

$$n_1 = n_2 = 2 \left[ \frac{(Z_\alpha + Z_\beta)s}{(X_1 - X_2)} \right]^2 = 2 \left[ \frac{(1.96 + 0.84) 0.04}{(0.032)} \right]^2$$

$$n_1 = n_2 = 24.5 \text{ subjects} \rightarrow 25 \text{ subjects per group}$$

Legend:

$n_1$  : Number of subjects in the intervention group (glutamine group)

$n_2$  : Number of subjects in the control group

$s$  : Standard deviation = 0.0415

$Z_\alpha$  : Z value in 95% confidence index = 1.96

$Z_\beta$  : Z value of test power = 0.84

$X_1 - X_2$  : Difference in mean value = 0.032

Assuming a 20% drop out event, the final sample size are:

$$n = 50 + (50 * 20\%)$$

$$n = 50 + 10$$

$$n = 60 \text{ subjects}$$

For a fixed sample size design, the sample size required to achieve a power of  $1-\beta=0.84$  for a two sided t-test at level  $\alpha=0.05$  under these assumptions amounts to a total of 60 patients, or 30 patients in each treatment group.

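### Two biomarkers are primary, troponin I at four post-CPB times, with no success rule, troponin summary or multiplicity control, so 5% control of the primary claim is not assured

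*Combined protocol and SAP*

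**What the plan says.** The Primary Endpoint section names two biomarkers: "Plasma glutamine before induction to anesthesia and 24 hours after CPB, and plasma troponin I before induction to anesthesia, 5 minutes, 6 hours", with troponin I continuing to 24 and 48 hours. The Study Summary words the troponin I part the same way: "plasma troponin I before induction to anesthesia, 5 minutes, 6 hours, 24 hours and 48 hours after CPB". That makes one post-CPB time for glutamine and four for troponin I.

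The decision rule is one sentence under Sample size calculations: "Results are considered statistically significant if" p is below 0.05. The same section sizes a single comparison: "The sample size of this study is obtained from the two-way hypothesis testing formula for the two mean values in two independent groups". Its legend gives "Difference in mean value = 0.032" without naming a biomarker, a time or a unit.

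The objectives do not settle which biomarker decides the trial:

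- The Objectives row of the Study Summary makes better clinical outcome primary and puts plasma glutamine level and myocardial damage in the secondary objective.
- The Purpose section makes glutamine level and myocardial damage part of the primary objective.
- Goals of the study puts troponin I under reducing myocardial damage ("as well as decrease of troponin I level") and glutamine under metabolism ("Improving myocardial metabolism by a decrease in plasma lactate levels, increase of plasma glutamine levels").

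**The concern.** Nothing in the supplied text turns these measurements into one primary result. It gives no troponin time, peak, area under the curve or repeated-measures contrast. It does not say how the pre-induction values enter, and it gives no either/both rule, testing order, alpha split or other adjustment. Data Collection describes sampling and assays, not analysis.

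The rule could therefore be settled after the results are seen. If p < 0.05 is applied to each listed result and any one is accepted, the chance of a false primary claim exceeds 5% unless the tests are perfectly correlated. Success on glutamine alone is also not excluded. Because the active arm is infused with a glutamine dipeptide, such a result would speak to exposure or metabolism, and on the plan's own grouping of goals not to myocardial damage. Power is uncertain too: one unnamed comparison was sized, so power to succeed on both biomarkers is not shown.

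**Working it through.** **Inputs.** From the plan: two-sided α = 0.05 (z = 1.96), power 80% (z = 0.84), difference 0.032, SD 0.04 in the formula and 0.0415 in the legend, one post-CPB glutamine time, four post-CPB troponin times. Assumed, because the plan does not give them: the success rule, and the correlation ρ between test statistics (0 to 0.9).

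**Step 1: the plan's own figure.** n per group = 2[(1.96 + 0.84) × 0.04 / 0.032]² = 2 × 3.5² = 24.5, so 25. Two groups make 50, and 50 × 1.2 = 60. This reproduces. With the legend SD of 0.0415 the formula gives 26.4, so 27. Either way it covers one comparison at 0.05.

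**Step 2: any one result suffices.** For k equicorrelated two-sided tests with no true effect,

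P(at least one) = 1 − ∫ [Φ((1.96 − √ρ·g)/√(1−ρ)) − Φ((−1.96 − √ρ·g)/√(1−ρ))]^k φ(g) dg.

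At ρ = 0 this is 1 − 0.95^k: 9.75% for k = 2, 18.5% for k = 4, 22.6% for k = 5. For four correlated troponin tests plus an independent glutamine test it is 1 − (1 − p₄) × 0.95, where p₄ is the four-test value.

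| Tests | ρ = 0 | ρ = 0.5 | ρ = 0.7 | ρ = 0.9 |
|---|---|---|---|---|
| One per biomarker (2) | 9.75% | 9.1% | 8.35% | 7.0% |
| Four troponin times | 18.5% | 15.6% | 13.0% | 9.4% |
| Four troponin + glutamine independent | 22.6% | 19.8% | 17.4% | 13.9% |

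In the last row ρ applies among the troponin times. Worked example at ρ = 0.9: 1 − (1 − 0.0936) × 0.95 = 0.1389. Simulation agrees to within 0.001. With no assumption on correlation, five tests lie between 5% (perfect correlation) and 5 × 0.05 = 25% (Bonferroni bound).

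**Step 3: both biomarkers required, one pre-set test each.**

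- Neither affected: P(both) = 0.05 + 0.05 − P(at least one). This is 0.10 − 0.0975 = 0.25% at ρ = 0 and 0.10 − 0.0704 = 3.0% at ρ = 0.9.
- Only one affected: at most 5%, because the other test must still be a false positive.

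**Step 4: both required, but any troponin time counts.** If glutamine truly rises and is detected with certainty, the joint error equals the four-troponin row: 9.4% (ρ = 0.9) to 18.5% (ρ = 0).

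**Step 5: power.**

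- Both required, with an assumed 80% for each test: P(both) = Φ₂(0.842, 0.842; ρ) = 64% at ρ = 0 (0.8 × 0.8) to 75% at ρ = 0.9.
- Either suffices at 0.025 each (z = 2.241), for the one comparison that was sized: 2[(2.241 + 0.842) × 0.04 / 0.032]² = 29.7, so 30 evaluable per group. With SD 0.0415 it is 32. The plan has 25. At SD 0.0415, power at 0.025 is 77% with 30 per group and 69% with 25.

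**The case against.** The strongest reply is that *and* in the Primary Endpoint section means both biomarkers must be positive, so no adjustment is needed. That is a fair reading, and with one pre-set test each it holds the error at 5% or less. But the plan does not say so, and the word cannot say how four troponin times become one test. If any of them counts, Step 4 applies, and a rise in glutamine is what the plan's own goals expect.

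A second reply is that the section lists sampling times, not tests, and that the sample-size section refers to one two-sided t-test. This stands in part. Five is the number of post-CPB comparisons listed, not a count of tests that the plan sets. The number could be one per biomarker, or more than five, since raw values and changes from baseline are both open.

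Third, glutamine level is a stated aim in its own right, and the Purpose section puts it first. This stands. A reader might infer that troponin I must outrank glutamine; the documents contradict each other on rank and do not support that.

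Fourth, serial troponin values in one patient are unlikely to be independent, so 22.6% is the extreme of the illustration. That also stands.

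**Conclusion.** The gap is real and bears on the trial's main conclusion: as written, a reader could not tell whether the primary endpoint was met, and 5% control is not assured. A reader might infer that the trial's false-positive rate is about 23%, or that it is certainly inflated. The documents support neither. The 7.0% to 22.6% span rests on an assumed any-one-suffices rule and assumed correlations, and a both-required rule with one pre-set test each would keep the error at or below 5%. The joint power of 64% to 75% rests on an assumed 80% per biomarker, which the plan does not show. Absence of a rule is judged on the supplied text, from which a few pages were removed; the endpoint and sample-size sections are present.

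**What to change.** Make these changes before any by-group analysis, including analysis by coded group. The Randomization section keeps data analysers blind to allocation, but two-sided p-values by coded group can be seen without breaking the blind, so fixing the rule before unblinding would be too late.

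1. Reconcile the objectives in the Study Summary and the Purpose section.
2. In the Study Summary and the Primary Endpoint section, fix a single troponin I analysis adjusted for the pre-induction value. Examples are the treatment effect averaged over the four post-CPB times from a repeated-measures model of log troponin I, or one named time. Report the individual times as estimates with 95% confidence intervals.
3. State one success rule:
   - both biomarkers significant at two-sided 0.05; or
   - a fixed sequence, order stated, each step at two-sided 0.05; or
   - if either is meant to suffice, a split alpha such as 0.025 each.
4. Under Sample size calculations, say which endpoint and time the 0.032 and the SD describe, and restate power for the chosen rule without enrolling more patients.

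The cost is wording only, since every time point is already collected. The price is power below that of a single test at 0.05 when both must pass or alpha is split (Step 5). In a fixed sequence, the second biomarker cannot be claimed if the first fails. Under any of the rules, an effect at only one unnamed troponin time could not be claimed as primary success.

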#### Secondary Endpoint

Alpha-Ketoglutarate, myocardial injury score, apoptosis index, anti-cardiac troponin I expression, ejection fraction, cardiac index, plasma lactate, intensive care unit ventilation time, intensive care unit length of stay and vasoactive inotropic score.

### **ASSESSMENT OF SAFETY**

Adverse events will be monitored and collected by the study team from the point of signed consent until the adverse event(s) are resolved and subjects are stabilized. For each adverse event, a detailed explanation will be obtained from the subject and subject's medical record. All adverse events will be recorded on the CRFs.

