### *Study Population and Selection Criteria*

All participants will be required to sign a written informed consent, be willing and able to comply with all study requirements and should meet the following criteria:

- Male and female patients, aged  $\geq$  18 years old with coronary heart disease indicated for elective coronary artery bypass grafting under cardiopulmonary bypass
- Left ventricle ejection fraction of 31-50%, confirmed by echocardiography or radionuclide imaging
- No history of heart surgery
- Agree to participate in the study and signed a written informed consent

Subjects will be **excluded** from the study based on the following criteria:

- Change of surgical plan from elective into emergency CABG surgery
- Additional procedures other than coronary artery bypass graft procedure
- Onset of myocardial infarction within the last three months
- Blood creatinine level  $> 2$  mg/dL
- ALT/AST level  $> 1.5x$  of normal value
- Use of preoperative intra-aortic balloon pump
- History of stroke with onset of less than 3 months
- Preoperative atrial fibrillation
- Heart conduction problem or pacemaker use
- Contraindications to pulmonary artery catheter insertion

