### *Adverse Reactions*

There is no expectation of any adverse outcomes or reactions, should there be any adverse outcome or reactions, necessary management and will be taken in accordance with the standard medical protocol at the National Cardiovascular Center Harapan Kita Hospital. All participants will be given access to contact information of the primary investigator performing this study. Any adverse reactions will be reported immediately to the primary investigator or co-investigators.

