### **Reasons for Withdrawal or Termination:**

A subject may be discontinued from the study at any time if the subject or the investigator feels that it is not in the subject's best interest to continue. The following is a list of possible reasons the subjects will be **dropped out** from the study:

- Stroke after surgery
- Perioperative myocardial infarction based on type 5 myocardial infarct criteria
- Haemorrhage complications requiring repeat surgery
- Use of continuous veno-venous hemofiltration or haemodialysis after coronary artery bypass graft surgery
- Delayed sternal closure
- Aortic cross-clamp duration of > 120 minutes and/or cardiopulmonary bypass duration of >180 minutes

All subjects are free to withdraw from participation at any time, for any reason, specified or unspecified, and without prejudice. Reasonable attempts will be made by the investigator to provide a reason for subject withdrawals. The reason for the subject's withdrawal from the study will be specified in the subject's source documents and the Case Report Form (CRF). If a subject is withdrawn from treatment due to an adverse event, the subject will be followed and treated by the investigator until the adverse event has resolved or stabilized.

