**Pre-Operative Laboratory Parameters**

Parameters	Value
Hb	
Hct	
Leukocyte	
Trombocyte	
SGOT	
SGPT	
Ur	
Cr	
Albumin	
pH	
pCO2	
pO2	
FiO2	
Na+	
K+	
HCO3-	
SatO2	
Lactate	
CRP	
HIV	
Hepatitis B	
Hepatitis C	

ECG:

CXR:

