**Research CRF Checklist**

Sample characteristics	
Preoperative laboratory parameters	
Surgical procedure, aortic cross-clamp and CPB	
Intervention liquid bottle number: _____	
Right atrial appendage tissue biopsy	

• a-KG level

• Myocardial injury score

• Apoptotic index

• Anti-cardiac troponin I expression

	
Plasma glutamine levels	
Troponin I levels	
Lactate levels	
Ejection Fraction	
Cardiac Index	
Post-operative vasoactive and inotropes	
Surgery duration, aortic cross-clamp duration, ICU care duration and ventilator usage duration	
Research sample outcomes	

Researcher: \_\_\_\_\_ Date: \_\_\_\_\_ Signature: \_\_\_\_\_

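### The plan promises to record every adverse event on the CRF, but the visible CRF has no structured adverse-event section and no renal or hepatic laboratory value after dosing

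*Combined protocol and SAP*

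**What the plan says.** Under Assessment of Safety, the study team is to collect adverse events "from the point of signed consent until the adverse event(s) are resolved and subjects are stabilized". The section continues: "For each adverse event, a detailed explanation will be obtained from the subject and subject's medical record", and then "All adverse events will be recorded on the CRFs".

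The section on reasons for withdrawal provides for toxicity that ends treatment: "If a subject is withdrawn from treatment due to an adverse event, the subject will be followed and treated by the investigator" until the event resolves or stabilises. It also requires the reason for any study withdrawal to be given in the source documents and on the CRF. The Adverse Reactions section says "There is no expectation of any adverse outcomes or reactions".

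The selection criteria exclude patients on renal and hepatic values ("Blood creatinine level" above 2 mg/dL, ALT/AST above 1.5 times normal). In the CRF appendix, SGOT, SGPT, urea and creatinine stand on the page headed "Pre-Operative Laboratory Parameters". The checklist that closes the CRF has one entry for complications, "Research sample outcomes".

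**The concern.** The safety rule and the form meant to carry it out do not match. The rule covers every event, explained in detail and followed to resolution. The form asks about a short list of complications chosen in advance, most of them complications of cardiac surgery. It has no field for linking an event to the infusion or for what was done with the infusion as a result.

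What is at stake is how a quiet safety record would be read. The protocol expects no adverse reactions, and a form without a structured place for unlisted events will tend to return few of them. A reader could not tell absence of harm from absence of recording. The protocol also says that its results can be applied in practice, so the harm side of the comparison should be as readable as the efficacy side.

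**Working it through.** The plan gives no figure on this point, so the check sets the safety rule beside the CRF pages and counts fields.

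**1. Adverse-event fields**

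| What the safety text needs | Where the visible CRF provides it |
|---|---|
| A record of any adverse event | Research Sample Outcomes page: 12 yes/no criteria and a free note |
| Onset | Time of death; onset for arrhythmia, intubation and IABP (4 of 12 criteria have a timing field) |
| Severity | No field |
| Relation to the infusion | No field |
| Action taken with the infusion | No field; the surgical page has one date and time for giving the intervention and a bottle number, but no end time or volume given |
| Outcome or resolution | No general field; durations for arrhythmia, intubation and IABP only |

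The first six of the 12 criteria repeat the protocol's drop-out criteria. The other six are mortality, sepsis, arrhythmia, acute renal failure, intubation and IABP use.

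**2. Checklist.** The CRF checklist has 13 entries: sample characteristics, pre-operative laboratory values, surgical procedure, bottle number, atrial tissue, glutamine, troponin I, lactate, ejection fraction, cardiac index, vasoactive drugs, durations, and outcomes. None is an adverse-event section, and none is a post-operative renal or hepatic laboratory section.

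**3. Renal and hepatic values.** The Methods of Intervention section starts the infusion after induction and runs it for 24 hours. All four relevant analytes are on the pre-operative page, which has a single value column. Analytes with a post-dose field: 0 of 4. The Data Collection section schedules post-CPB troponin I, glutamine and lactate, but no creatinine, urea or transaminase.

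**4. Organ events among the 12 criteria.** Renal: 2 (acute renal failure; need for CVVH or haemodialysis). Hepatic: 0. The acute renal failure item has no definition, value, onset or grade.

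**5. What happens to the renal signal.** A patient who needs CVVH or haemodialysis meets a drop-out criterion. The section on handling withdrawals has the CRF completed only to the last visit performed. The SAP names no safety endpoint, safety population or table of events by arm. Even the crude renal items have no stated route into an analysis.

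**The case against.** The best reply is that the CRF is not silent on harm. The outcomes page records death with time and cause, arrhythmia with onset, type and duration, intubation with onset, duration and reason, and IABP use with onset and duration. It also records sepsis and two renal events. It ends with a free note, and the protocol requires the reason for withdrawal on the CRF. All of this stands. A reader might infer that a site cannot record an infusion reaction or a laboratory rise at all, or that toxicity as a whole cannot be assessed. The documents do not support either reading: unlisted events can go in the note, and major complications, including gross renal harm, can be compared by arm. What is missing is structure, attribution and laboratory data.

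A second reply is that the visible CRF may be incomplete. The checklist names glutamine, troponin I and lactate, yet no pages for the first two or for post-operative lactate are shown, and some material is absent from the public copy. This is a fair caution. It is weakened because the checklist names those items and does not name an adverse-event section or post-operative renal or hepatic tests.

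A third is that the documents give no reason for the creatinine and ALT/AST exclusions. A reader might infer that they guard against toxicity of the infusion; the text does not say so. They show only that the plan treats renal and hepatic function as relevant to taking part.

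It is also tempting to attach an upper limit on event rates from zero events. Such a limit follows from group size alone and would be the same with a perfect form, so it does not measure this defect.

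**Conclusion.** The point holds in a limited form. The SAP commits to recording all adverse events on the CRF, while the visible CRF provides a complication list with limited timing fields and an unstructured note. In size: no adverse-event section among 13 checklist entries, no field for severity, relation to the infusion or action taken with it, no post-dose value for any of four renal and hepatic analytes, and no hepatic item among 12 outcome criteria. Hepatic effects and graded or laboratory-level renal change cannot be assessed from the CRF. Gross renal harm can be seen, but only as an undefined tick and a CVVH/haemodialysis tick.

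This rests on the checklist being a fair list of the CRF's sections; a separate adverse-event form outside the public copy would remove much of the point. The primary comparison is not threatened. The change should be made because the plan's own safety rule lacks a form to carry it out.

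**What to change.** - Add one adverse-event log page to the CRF and its checklist: event, onset relative to the start of infusion, severity, relation to the infusion, action taken with the infusion, outcome.
- Add post-infusion fields for SGOT, SGPT, urea and creatinine, transcribed from the hospital record where measured. The documents do not say how often these are measured after surgery, so report the number of patients with a value in each arm.
- State the criterion behind the acute renal failure tick.
- Add to the SAP a table of events by arm for everyone who received any infusion, including patients dropped out under the protocol's criteria.

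The cost is an added CRF page, some transcription, and ethics approval, which the protocol requires for any amendment. No new visit or procedure is needed. The protocol limits the collection of personal information to what the research aims need; the log fits within that, since the plan already commits to recording these events.
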